### 13.3 General Principles of Statistical Analysis

The primary outcome was one-tailed test at significance levels of 0.025. All the other statistical analyses were two-tailed tests, at a significant level of 0.05, using SAS software, version 9.4 (SAS Institute Inc, Cary, North Carolina, USA). For measurement data, mean±standard deviations (M±SD), median, minimum, maximum, were presented. Differences between groups were compared using group t tests or nonparametric tests. Comparisons with the baseline used paired t tests or nonparametric tests. For counting data, cases and percentages were presented, and differences between groups were compared using Chi-squared tests, Fisher's exact probabilities or non-parameters tests. For abnormal distributed data, differences between groups were compared using nonparametric tests. Missing data for the primary outcome were imputed using the multiple imputation (MI) method under the missing at random assumption for the mITT population. The results for the PP set were used as the sensitivity analysis for the multiple imputation. For secondary outcomes, no imputation was used and observed data were used for analyzing.

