### 2.4.2 Sample Size Calculation

The primary outcome is the proportion of participants with 3 or more mean weekly CSBMs over weeks 3-8. According to our previous 60-size pilot study, the proportion was 31.67% by EA; and the proportion by prucalopride was 30.9% 6. The non-inferiority sample size calculation formula is listed as below:

$$\begin{split} n &= \frac{(Z_{1-\alpha} + Z_{1-\beta})^2 [p_1(1-p_1) + p_2(1-p_2)]}{(\epsilon - \delta)^2} \\ &= \frac{(1.645 + 0.845)^2 [0.3167 \times (1 - 0.3167) + 0.309 \times (1 - 0.309)]}{[0.3167 - 0.309 - (-0.1)]^2} = 230 \end{split}$$

To assess the non-inferiority between the treatment and control groups, a sample size of 276 for each group will be sufficient, with a non-inferior margin of -10%, one-sided significance level of 5% and a power of 80%, allowing for a 20% dropout. In this trial, we aim to recruit 560 participants considering the balance of 14 centers, with 40 participants of each center.

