#### 7.3 Statistical Methods

The data from the 14 centers will be pooled, and the Institute of Basic Research in Clinical Medicine, China Academy of Chinese Medical Sciences in Beijing will conduct the statistical analysis using the SAS 9.4 (SAS Institute, Cary, NC, US) software. All statistical analyses will be two-sided tests except for the primary outcome (one-sided). The level of significance will be established at 0.05. Continuous data will be represented by the mean (standard deviation), mean [95% confidence interval (CI)], or median (interquartile range); categorical data will be represented by percentages. To compare two independent samples, a t-test or nonparametric test will be used for continuous data, and a chi-square test/the Fisher exact test/non-parametric tests will be used for categorical data. For the primary outcome, the CMH test will be used to avoid the center effect.

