### 9. Sample Size Calculation

The primary outcome is the proportion of participants with 3 or more mean weekly CSBMs over weeks 3-8. According to our previous 60-size pilot study, the proportion was 31.67% by EA; and the proportion by prucalopride was 30.9% 6. The non-inferiority sample size calculation formula is listed as below:

$$\begin{split} n &= \frac{(Z_{1-\alpha} + Z_{1-\beta})^2 [p_1(1-p_1) + p_2(1-p_2)]}{(\epsilon - \delta)^2} \\ &= \frac{(1.645 + 0.845)^2 [0.3167 \times (1 - 0.3167) + 0.309 \times (1 - 0.309)]}{[0.3167 - 0.309 - (-0.1)]^2} = 230 \end{split}$$

To assess the non-inferiority between the treatment and control groups, a sample size of 276 for each group will be sufficient, with a non-inferior margin of -10%, one-sided 5% level of significance, a power of 80% and allowing for a 20% dropout. In this trial, we aim to recruit 560 participants considering the balance of 14 centers, with 40 participants of each center.

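### The primary non-inferiority test has two significance levels (one-sided 0.025 in SAP 13.3; one-sided 0.05 in SAP 9 and protocol 2.4.2 and 7.3), and the stated 80% power holds only at 0.05

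*Supplement*

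**What the plan says.** Four current sections give a significance level for the primary outcome.

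- **SAP 13.3** (analysis principles): "The primary outcome was one-tailed test at significance levels of 0.025".
- **SAP 9** (sample size): "with a non-inferior margin of -10%, one-sided 5% level of significance, a power of 80% and allowing for a 20% dropout". The printed formula uses 1.645.
- **Final protocol 2.4.2** (sample size): "one-sided significance level of 5% and a power of 80%, allowing for a 20% dropout", with the same formula.
- **Final protocol 7.3** (methods): "All statistical analyses will be two-sided tests except for the primary outcome (one-sided). The level of significance will be established at 0.05".

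Both sample size sections arrive at 230 per group, raise this to 276 for dropout ("a sample size of 276 for each group will be sufficient"), and set recruitment at 560 across 14 centres. SAP 13.3 also provides for multiple imputation of missing primary outcome data, assuming missing at random, in the mITT set. SAP 13.2 defines that set as randomised participants with baseline data. No section recalculates the sample size or the power at 0.025.

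**The concern.** The significance level is the decision rule for the trial's main claim, and the documents give two. Protocol 7.3 cannot be read as a two-sided 0.05 for the primary outcome: it exempts that outcome from two-sided testing, and the 1.645 in the formula confirms one-sided 5%. A rule that the SAP prevails over the protocol would not settle the matter either, because SAP 9 and SAP 13.3 disagree within one document.

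Two things are at stake. A result in the gap between the thresholds could be reported as non-inferior or as inconclusive, depending on the section followed. And if 0.025 governs, the stated 80% power belongs to a test that will not be performed.

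**Working it through.** **Inputs** (SAP 9 and protocol 2.4.2 unless noted): EA response 0.3167; prucalopride response 0.309; margin -0.10; power 80%; dropout 20%; 560 recruited. Allocation is 1:1 (SAP 4), so 280 per group. One-sided level: 0.05 (SAP 9, protocol 2.4.2 and 7.3) or 0.025 (SAP 13.3).

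Variance term: 0.3167 × 0.6833 + 0.309 × 0.691 = 0.4299. 
Distance from the assumed difference to the margin: 0.0077 + 0.10 = 0.1077.

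**1. The plan's own figure.** n = (1.645 + 0.845)² × 0.4299 / 0.1077² = 229.8, so 230 per group. It reproduces at one-sided 0.05.

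**2. Size needed at 0.025.** Replacing 1.645 by 1.96 gives about 291 evaluable per group for 80% power. That is more than the 280 per group to be randomised, before any dropout. Allowing for 20% loss, 291 / 0.8 = 363.75, so 364 per group or 728 in total.

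**3. Power at each level.** Power = Φ(0.1077 / √(0.4299 / n) − z), with z = 1.645 or 1.96.

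| Information per group | One-sided 0.05 | One-sided 0.025 |
|---|---|---|
| 221 (276 × 0.8) | 78.7% | 68.5% |
| 224 (280 × 0.8) | 79.2% | 69.1% |
| 230 (plan's target) | 80.1% | 70.2% |
| 280 (nothing lost) | 86.5% | 78.5% |

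At 230 per group the change of level costs 80.1 − 70.2 = 9.9 points.

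**4. Sensitivity to the assumed advantage.** The calculation credits EA with a true advantage of 0.77 points. If both true rates are 30.9%, the variance term is 2 × 0.309 × 0.691 = 0.4270 and the distance is 0.10. Power at 0.025 is then 62.9% with 224 per group and 72.6% with 280.

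**5. Width of the disputed zone.** With 224 per group the standard error is √(0.4299 / 224) = 0.0438, or 4.38 points. The observed difference (EA minus prucalopride) must exceed about -10 + 1.645 × 4.38 = -2.8 points at 0.05, and about -10 + 1.96 × 4.38 = -1.4 points at 0.025. Results between these limits pass one text and fail the other. At the plan's assumptions the chance of landing there is 79.2 − 69.1 = 10.1 points.

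**6. Dropout inflation, taken separately.** 276 = 230 × 1.2, and 276 × 0.8 = 220.8, short of 230. Dividing instead gives 230 / 0.8 = 287.5, so 288 per group (576 in total). Because 560 are recruited rather than 552, 224 per group remain, and power at 0.05 is 79.2%. This slip alone costs about one point.

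**The case against.** The strongest reply is that the SAP's analysis section is the operative rule. Protocol 6.8 requires the SAP to be approved before database lock, and 0.025 is the stricter of the two levels, so applying it does not inflate the type I error of the non-inferiority claim. On this view the 5% in SAP 9 only records how the trial was sized. The point about type I error stands: under SAP 13.3 the cost is a greater chance of an inconclusive trial, not a false claim. But SAP 9 is part of the same final SAP and is not labelled as a historical calculation, and protocol 7.3 states 0.05 as an analysis level. The texts still conflict.

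A second reply concerns size. A reader might infer that the true power is simply 69%. The documents do not support that as a single figure: it treats the 20% who drop out as contributing nothing, whereas SAP 13.3 imputes their primary outcome. How much information imputation recovers cannot be known from the documents, so only a range can be given. Its upper end, 78.5%, is 1.5 points below target.

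A reader might also blame the multiplied dropout allowance for the shortfall. The table shows otherwise: nearly all of it comes from the change of level.

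**Conclusion.** The contradiction is real and the text is wrong as written. The primary decision threshold is stated as both 0.025 and 0.05 in current sections, and the claim of 80% power is not met at 0.025 under any dropout assumption with 560 recruited. Power at that level lies between about 69% and 78.5%, depending on the information lost to dropout. The lower end falls to about 63% if EA has no true advantage.

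These figures rest on the plan's own response rates, margin and unstratified formula, with unpooled variance and equal groups; any effect of stratifying the CMH test by centre is not counted. The threshold must be settled before the data are seen, because it can reverse the conclusion. The dropout arithmetic deserves correction but is a minor note.

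**What to change.** 1. State one threshold in SAP 9, SAP 13.3 and final protocol 2.4.2 and 7.3: one-sided 0.025, equivalent to the lower limit of the two-sided 95% confidence interval for EA minus prucalopride lying above -10 points. This keeps the level in the SAP's analysis section and cannot be seen as loosening the criterion.
2. Keep 560 participants.
3. In SAP 9 and protocol 2.4.2, do one of two things. Either replace 1.645 by 1.96 in the formula, giving about 291 evaluable per group for 80% power, and say that 280 per group does not reach this. Or keep the 230 calculation, expressly labelled as a design-stage figure at one-sided 5%.
4. With either choice, restate power at 0.025 as about 69% (224 per group, no information from dropouts) to 78.5% (280 per group, none lost).
5. If the 5% calculation is kept, correct its dropout step to 230 / 0.8 = 288 per group, under the same 5% label. Do not carry 230 or 288 unlabelled into text that states 0.025.

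The cost is wording, plus a less favourable stated power. No additional participants and no change to conduct are needed.

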#### 13. Statistical Analysis

### 13.1 Objective and Hypothesis

#### Objective

Through comparing the efficacy of EA and prucalopride, we aim to evaluate if the effect of EA will be non-inferior to that of prucalopride. We also will evaluate if the therapeutic effect of EA could sustain for 3~6 months.

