#### 13.6 Secondary Outcomes

- (1) For the proportion of participants with 3 or more mean weekly CSBMs, the Cochran-Mantel-Haenszel (CMH) test, stratified by center, was used to test a hierarchical comparison between two groups. Assessing timeframe: weeks 1-2, 11-12, 15-16, 19-20, 31-32.
- (2) For the proportion of participants with ≥1 increase of mean weekly CSBMs from baseline, the Cochran-Mantel-Haenszel (CMH) test, stratified by center, was used to test a hierarchical comparison between two groups. Assessing timeframe, weeks 1-2, 3-8, 11-12, 15-16, 19-20, 31-32.
- (3) For the change from baseline in mean weekly CSBMs, a repeated measures analysis of variance was used, setting group, time, and the interaction of group and time as the fixed effects; besides, the baseline CSBMs data and usage of rescue medicine were set as the covariate. Assessing timeframe: weeks 1-2, 3-8, 11-12, 15-16, 19-20, 31-32.
- (4) For the change from baseline in mean weekly SBMs, the same statistical analysis was conducted in accordance with the change from baseline in mean weekly CSBMs. Assessing timeframe: weeks 1-2, 3-8, 11-12, 15-16, 19-20, 31-32.
- (5) For the mean scores of straining, the Wilcoxon rank-sum test was used. Assessing timeframe: weeks 1-2, 3-8, 11-12, 15-16, 19-20, 31-32.
- (6) For the mean scores of stool consistency, the Wilcoxon rank-sum test was used. Assessing timeframe: weeks 1-2, 3-8.
- (7) For the time to the first CSBM (counting by days), the Wilcoxon rank-sum test was used.
- (8) For the change in mean scores of PAC-QOL between two groups, t test was used. Assessing time point: week 4 and week 8.
- (9) Rescue medicine usage: For the proportion of participants using rescue medicine (bisacodyl or glycerine enema), the Chi-square test was used. For the average dosage of bisacodyl or glycerine enema used per week, the Wilcoxon rank-sum test was used. Assessing timeframe: weeks 1-2, 3-8, 11-12, 15-16, 19-20, 31-32.

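### SAP 13.3 and 13.6 judge 36 to 46 secondary between-arm comparisons each at two-sided 0.05, with no order, adjustment or exploratory label, and no endpoint is named for the sustained-effect objective

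*Supplement*

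**What the plan says.** The SAP names one primary contrast, the weeks 3-8 responder proportion for electro-acupuncture (EA) against prucalopride, and SAP 13.3 gives it its own level: "The primary outcome was one-tailed test at significance levels of 0.025". For all remaining analyses the same section says: "All the other statistical analyses were two-tailed tests, at a significant level of 0.05". Final protocol 7.3 is no more specific: "All statistical analyses will be two-sided tests except for the primary outcome (one-sided). The level of significance will be established at 0.05".

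SAP 13.6 (1) to (9) assigns between-arm tests to nine secondary outcomes, most of them over several windows. Item (1) covers five ("Assessing timeframe: weeks 1-2, 11-12, 15-16, 19-20, 31-32") and item (2) covers six ("Assessing timeframe, weeks 1-2, 3-8, 11-12, 15-16, 19-20, 31-32"). Items (3) and (4) use a model: "For the change from baseline in mean weekly CSBMs, a repeated measures analysis of variance was used", with group, time and their interaction as fixed effects. Only item (10) carries a non-confirmatory label (post-hoc).

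SAP 13.1 adds a second objective: "We also will evaluate if the therapeutic effect of EA could sustain for 3~6 months". SAP section 1 words it as three months or six months. Neither place names the outcome that would decide it.

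**The concern.** A per-test level of 0.05 is the error rate of one comparison chosen in advance. It is not the error rate of a claim picked afterwards from a list of several dozen. The plan does not say which kind of statement the secondary p-values may support, so a reader of the report could take any value below 0.05 as an established difference between the arms, whatever the primary result.

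This matters most for the sustained-effect objective. It is a declared aim of the trial, yet several bowel-movement outcomes at several follow-up windows could each be put forward as its answer. Without a named outcome and window, the choice can be made after the results are seen.

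**Working it through.** The documents state no family-wise error rate and no count of secondary tests, so there is no figure of the plan's own to reproduce.

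**Count of between-arm comparisons, SAP 13.6 (1) to (9)**

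| Item | Windows or time points | Comparisons |
|---|---|---|
| (1) Three or more weekly CSBMs | 5 | 5 |
| (2) Increase of at least one CSBM | 6 | 6 |
| (3) Change in CSBMs, repeated measures | 6 | 6 (or 1) |
| (4) Change in SBMs, repeated measures | 6 | 6 (or 1) |
| (5) Straining | 6 | 6 |
| (6) Stool consistency | 2 | 2 |
| (7) Time to first CSBM | 1 | 1 |
| (8) PAC-QOL | 2 | 2 |
| (9) Rescue use: proportion and dosage | 6 each | 12 |

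- Every window counted: 5 + 6 + 6 + 6 + 6 + 2 + 1 + 2 + 12 = 46.
- One overall group test per model in (3) and (4): 46 − 12 + 2 = 36.

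The count leaves out the post-hoc analyses in (10), the within-arm comparisons with baseline in 13.3 and the safety tests in 13.7. Testing bisacodyl and enema dosage separately would add six, giving 52.

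**Expected false positives if the arms do not differ** (number of tests × 0.05; no correlation needed)

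- 36 × 0.05 = 1.8
- 46 × 0.05 = 2.3

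**Chance of at least one false positive**

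For m independent tests the chance is 1 − 0.95^m:

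- m = 46: 1 − 0.95^46 = 0.906
- m = 36: 1 − 0.95^36 = 0.842

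For correlated tests I assumed normal statistics with a common pairwise correlation ρ, Z_i = √ρ·S + √(1−ρ)·E_i, each rejected when |Z_i| > 1.96. The shared factor S is integrated out. The documents give no ρ, so the range is shown:

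| ρ | 46 tests | 36 tests |
|---|---|---|
| 0 | 91% | 84% |
| 0.3 | 78% | 72% |
| 0.5 | 60% | 55% |
| 0.6 | 50% | 45% |
| 0.7 | 39% | 36% |
| 0.9 | 19% | 18% |

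Simulation agrees with these values to within rounding. A structured pattern for the 46 tests, with correlation 0.3 to 0.9 across windows and 0 to 0.8 across outcomes, gives 31% to 88%.

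**Sustained-effect objective**

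- Items (1) to (4), the CSBM and SBM outcomes, at all four follow-up windows: 4 × 4 = 16 candidate comparisons.
- EA ends at week 8, so weeks 19-20 and 31-32 close 20 − 8 = 12 and 32 − 8 = 24 weeks later. If three and six months mean these two windows, there are 4 × 2 = 8 candidates. The SAP does not state this mapping; it is my inference.
- Chance of at least one false positive at ρ = 0.5, by the same formula: 25% for 8 and 37% for 16.

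**Is there a testing order elsewhere?** SAP 13.5 and 13.6 use the word *hierarchical*, but for the centre-stratified Cochran-Mantel-Haenszel comparison. That describes stratification, not a sequence of hypotheses.

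**The case against.** Several points on the other side have force.

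- **Likelihood.** A reader might infer that a false positive is more likely than not, at about 60%. The documents do not support that as a finding. It needs an assumed common correlation of 0.5, and the chance falls to one half or less from about 0.6 with 46 tests (about 0.55 with 36). High correlation is plausible for many pairs: outcomes (1) to (3) come from the same CSBM diary counts, and CSBMs are a subset of SBMs. What stands is the range and the expected number.
- **Count.** Items (3) and (4) specify models and state no contrast at each window. Forty-six is therefore an upper reading of these items, and 36 to 46 is the fair statement.
- **Follow-up window.** The three- or six-month wording points towards windows, so it goes too far to say that the plan gives no indication of one, and 16 is an upper count. The objective may also be read as a within-arm question, for which SAP 13.3 provides paired comparisons with baseline. Even so, neither an outcome nor one of these readings is fixed.
- **The null in follow-up.** EA has stopped while prucalopride continues in participants without the listed cardiac findings, so equal arms may be an unlikely state there. The rates above assume no difference anywhere and are a worst case in that sense.
- **No planned claim.** Formal hypotheses are written only for the primary, and the original protocol's remark about possible superiority of EA in follow-up is absent from the final protocol and the SAP. A reader might infer that the plan intends to declare secondary differences even after a failed primary. No text says so. The risk lies in reporting, and the plan leaves it open.

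**Conclusion.** The point holds as a minor one. The SAP states a rule of two-sided 0.05 per test and applies it to 36 to 46 secondary between-arm comparisons, without order, adjustment, gatekeeping or an exploratory label. The stated 5% is then not the error rate behind a conclusion selected from that list.

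The size that needs no correlation assumption is 1.8 to 2.3 expected false positives if the arms do not differ. The chance of at least one runs from 18% to 91% over common correlations from 0.9 to 0 and counts from 36 to 46; no single value in that range can be read from the documents. For the sustained-effect objective, 8 to 16 CSBM and SBM comparisons could serve, with a 25% to 37% chance of a false positive at an assumed correlation of 0.5.

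A reader might infer that the non-inferiority conclusion itself is compromised. It is not: the primary is a single pre-specified comparison, and the number of secondary tests does not change its type I error.

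**What to change.** In SAP 13.3, replace the general 0.05 rule for non-primary analyses with a statement to this effect, and repeat it in protocol 7.3:

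- The primary non-inferiority comparison is the only confirmatory test.
- Secondary outcomes, at all windows, are exploratory. They are reported as between-group differences with 95% confidence intervals and p-values not adjusted for multiplicity.
- No conclusion of superiority or difference is drawn from them.

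If the sponsor wants a formal claim of sustained effect, the SAP should name one outcome, for example the proportion with three or more weekly CSBMs. Its follow-up windows should be tested in a pre-stated fixed order at two-sided 0.05, only after the primary succeeds and stopping at the first failure. This fixed sequence needs no splitting of alpha.

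The cost is one paragraph in the SAP and one sentence in the protocol, with no new data, participants or analyses. The downside is that isolated secondary p-values below 0.05 can no longer be presented as established differences.

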### 2.4.5.1 Inclusion Criteria:

- 1) Primary chronic constipation meeting the Rome III criteria, with ≤2 mean weekly CSBMs (CSBM refers to the bowel movement without the help of drug or hands within the past 24 hours with the feeling of complete evacuation. A bowel movement beyond 24 hours after the use of medicine/hands also could be considered an SBM) in the past three months. Participants should also meet at least one of the following criteria: a) a feeling of straining during evacuation (at least once 4 bowel movements); b) lumpy or hard stools (at least once per 4 bowel movements); c) a feeling of incomplete evacuation after a bowel movement (at least once per 4 bowel movements); d) a feeling of obstruction in the anus/rectum (at least once per 4 bowel movements); e) needing the help of medication or hands for evacuation (at least once per 4 bowel movements).
- 2) Does not meet the diagnostic criteria for irritable bowel syndrome (IBS).
- 3) Previous laxative use failed to provide satisfactory relief.
- 4) Participants aged 18 to 75 years old.
- 5) Two or fewer CSBMs per week during the 2-week baseline assessment (run-in) period.
- 6) No use of medicine for constipation during the 2 weeks before enrolment (except rescue medication usage); no acupuncture treatment for constipation in the previous 1 month; no participation in any other on-going trial.
- 7) Volunteered to join this trial and signed informed consent.

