### 2.4.5.2 Exclusion Criteria:

- 1) Irritable bowel syndrome, organic constipation or secondary constipation caused by endocrine, metabolic, nervous, postoperative diseases, or drugs;
- 2) More than one mushy or watery stool during baseline while not taking laxatives (Bristol stool type 6 or 7);
- 3) A history of pelvic floor dysfunction;
- 4) Taking medicine that can influence the intestinal function or induce constipation (However, during the trial, participants are allowed to take drugs for other diseases which may affect the evaluation of the efficacy, the usage of the drugs should be recorded in detail)
- 5) Severe haemorrhoid or anal fissure;
- 6) Participants with severe cardiovascular, hepatic or renal diseases, cognitive impairment, abdominal aortic aneurysm or hepatosplenomegaly, aphasia, mental disorders, or illness that will influence the examination or treatment;
- 7) Women in the gestation or lactation period;
- 8) Participants with blood coagulation disorders or taking anticoagulants regularly, such as Warfarin and Heparin;
- 9) Participants with a cardiac pacemaker.

\*Notes for the screening and baseline evaluation (run-in) period: ① Medical history and physical examination were needed. Secondary constipation should be noticed if any symptom or sign of medical history suggests that constipation may be secondary; ② Colonoscopy is recommended for participants ≥50 years; ③ Colonoscopy may also be needed if any of the following alarming signs or/and symptoms occurs in any age: gastrointestinal bleeding, anemia, progressive weight loss, abdominal mass, significant abdominal pain, history of colon polyps especially in participants with family history of colorectal cancer; ④ The stool routine test and occult blood test must be done in each prospective case; ⑤ Baseline assessment (run-in) for 2 weeks: participants should discontinue laxatives or other medications and measures for constipation (except for rescue medicine) and maintain the usual diet and lifestyle. During baseline assessment (run-in) period, participant's gender, age, course of constipation, previous treatment for constipation, bowel movements, spontaneous defecation or not, complete evacuation or not, stool consistency, degree of straining, rescue medicine usage will be recorded

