#### **6.1 Inclusion Criteria**

- 1) Primary chronic constipation meeting the Rome III criteria with  $\leq$ 2 mean weekly CSBMs (CSBM refers to the bowel movement without the help of drug or hands within the past 24 hours with the feeling of complete evacuation. The bowel movement beyond 24 hours after the use of medicine/hands also could be considered an SBM) in the past three months. They should conform to at least one of the following items at the same time: a) a feeling of straining during evacuation (at least once per 4 bowel movements); b) lumpy or hard stools (at least once per 4 bowel movements); c) a feeling of incomplete evacuation after a bowel movement (at least once per 4 bowel movements); e) needing the help of hands for evacuation (at least once per 4 bowel movements).
- 2) Conditions for the diagnosis of irritable bowel syndrome (IBS) are inadequate.
- 3) Previous laxative use failed to provide satisfactory relief.
- 4) Participants aged 18 to 75 years old.
- 5) Two or fewer CSBMs per week during the 2-week baseline assessment (run-in) period.
- 6) No use of medicine for constipation during the 2 weeks before enrolment (except rescue medication usage); no acupuncture treatment for constipation in the previous 1 month; no participation in any other on-going trial.
- 7) Volunteered to join this trial and signed the informed consent.

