### 8. Research Period

The whole research period is 34 weeks, including 2-week baseline assessment (run-in) period (week -2, week -1), 8-week treatment period (weeks 1–8), and 24-week follow-up period (weeks 9–32). The time frame of the trial is presented in Figure 1.

Outcome assessing points: 1) baseline assessment (run-in) period: the last day of week -2 and week -1 (baseline evaluation); at week 0, the randomization and the first treatment will be carried out in one day. 2) Treatment period: the last day of week 2, week 4, week 6, week 8. 3) Follow-up period: the last day of week 12, week 16, week 20, week 32.

[figure not shown]

Figure 1 Research period and assessing point

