#### 10. Subject Evaluations and Outcomes

#### 10.1 Baseline Evaluations

Outcomes contain the complete spontaneous bowel movements (CSBMs), spontaneous bowel movements (SBMs), stool consistency (according to Bristol Stool Scale), straining during the defecation, rescue medicine used, and the form of Chinese-version Patient Assessment of Constipation Quality of Life (PAC-QOL). Participants will record their bowel movements, constipation-related symptoms, medicine used for constipation every day through week -2, week -1, weeks 1-8, weeks 11-12, weeks 15-16, weeks 19-20, and weeks 31-32. In both groups, participants without bowel movements (BMs) for 3 or more consecutive days were allowed to use bisacodyl (5-10mg a day before bedtime, Boehringer Ingelheim) or 110 ml glycerol enema as rescue medicine with documentation (time, dosage, and frequency of use) in the stool diary.

The SBMs are the bowel movements that occur in the absence of rescue medicine, or other assistant methods (laxatives, enemas, suppositories usage, or digging out by fingers) within the preceding 24 hours, which include the CSBMs. When participants used rescue medicine, or other measures for constipation, the defecation within 24 hours was considered a non-spontaneous bowel movement, whereas defecation exceeding 24 hours was deemed an SBM. CSBMs were the SBMs with the sensation of complete evacuation.

Outcome record time point: Baseline (the last day of week -2 and week -1), week 2, week 4, week 6, week 8, week 12, week 16, week 20, and week 32 (Figure 1).

[figure not shown]
Outcome assessing time frame: baseline period (weeks -2 to week -1), the latter 6-week treatment (weeks 3-8), the first 2-week treatment (weeks 1-2), and the follow-up periods (weeks 11-12, weeks 15-16, weeks 19-20, weeks 31-32).

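### SAP 13.3 allows within-arm paired tests against the run-in weeks used to select patients for few CSBMs, so regression to the mean alone can make them significant

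*Supplement*

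**What the plan says.** - **The test.** SAP 13.3: "Comparisons with the baseline used paired t tests or nonparametric tests". The same section sets the level: "All the other statistical analyses were two-tailed tests, at a significant level of 0.05". It names no outcome or window for the paired tests and does not label them descriptive.
- **Selection.** SAP 6.1, item 5 requires: "Two or fewer CSBMs per week during the 2-week baseline assessment (run-in) period". Item 1, also in the final protocol (2.4.5.1), adds a three-month history criterion, "with ≤2 mean weekly CSBMs".
- **Baseline.** SAP 8 treats run-in and baseline as one period, "including 2-week baseline assessment (run-in) period (week -2, week -1), 8-week treatment period (weeks 1–8". SAP 10.1 confirms it: "Outcome assessing time frame: baseline period (weeks -2 to week -1".
- **Objective.** SAP 13.1: "We also will evaluate if the therapeutic effect of EA could sustain for 3~6 months". No hypothesis or margin is attached to this objective.
- **Other analyses.** SAP 13.5 and 13.6 assign each efficacy outcome a between-group method: CMH stratified by center, repeated-measures ANOVA, rank-sum, t or chi-square tests. None of them is a paired test or a named within-EA contrast.

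**The concern.** A paired test against baseline tests whether the mean change from weeks -2 and -1 is zero. That differs from testing whether EA has no effect. The entry rule keeps people whose run-in count happened to be low and removes people whose count happened to be high. The baseline of those admitted therefore lies below their own long-run average, and later counts are expected to rise with no treatment effect. This would happen in both arms.

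It matters because of the sustained-effect objective. EA stops at week 8 while prucalopride may continue for a further 24 weeks, so the between-arm comparisons at weeks 11-32 contrast EA stopped with drug continuing. The paired tests in 13.3 are then the only explicitly planned tests of EA against its own baseline. A significant result at weeks 19-20 or 31-32 could be cited as proof that the effect lasts, although an inert treatment could produce it.

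**Working it through.** **Inputs from the documents.** The point itself concerns no stated figure; the arm size comes from SAP 9. That calculation reproduces: (1.645 + 0.845)² × [0.3167 × 0.6833 + 0.309 × 0.691] / 0.1077² = 229.8, so 230 per arm, and 230 × 1.2 = 276. The recruitment target of 560 at 1:1 gives 280 per arm, or 280 × 0.8 = 224 after 20% dropout.

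**Assumptions.** The documents give no distribution of true CSBM rates and no within-patient variance. Both are assumed and varied. Each patient has a constant true weekly rate, counts are Poisson, and treatment has no effect. Baseline is the mean of the two run-in weeks; follow-up is the mean of two later weeks, as for weeks 31-32. A trial counts as positive if the two-sided 5% paired t test is significant in the direction of improvement (nominal 2.5%).

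**Two readings of item 5.** The limit may apply to each run-in week or to the 2-week average. The words fit the first more directly, but item 1 of the same list uses a mean weekly count, so both are shown.

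**Case checkable by hand: all rates 0.5, n = 280.**

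*Each week at most 2.*
- Mean admitted count = (0.5 + 2 × 0.125) / (1 + 0.5 + 0.125) = 0.75 / 1.625 = 0.4615; drift = 0.5 − 0.4615 = +0.0385 per week.
- Variance of one admitted week = 1/1.625 − 0.4615² = 0.402. Variance of change = 0.402/2 + 0.5/2 = 0.451, so SD = 0.672.
- SE = 0.672/√280 = 0.0401; drift/SE = 0.96. P(improvement) ≈ 1 − Φ(1.96 − 0.96) ≈ 16%.

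*Two-week total at most 4.*
- Mean total = 2.6667/2.7083 = 0.9846, or 0.4923 per week; drift = +0.0077.
- SD of change ≈ 0.696, SE = 0.0416, drift/SE ≈ 0.19. P(improvement) ≈ 1 − Φ(1.77) ≈ 4%.

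**Simulated share of null trials declaring improvement, n = 280.**

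| Assumed true weekly rates | Limit on each week | Limit on 2-week average |
|---|---|---|
| Uniform 0 to 2 | 99% | 81% |
| 2 × Beta(1,3), mean 0.5 | 41% | 12% |
| All 0.5 | 16% | 4% |
| All 0.3 | 4% to 5% | about 2.5% |

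In the first row, each-week reading, the mean rises from 0.66 to about 0.87 CSBMs per week. At n = 224 the first three each-week figures are about 98%, 33% and 13%. Counts with half the Poisson variance reduce the first row to about 63% (each week) and 36% (average).

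**Second check with other assumptions.** This used Gamma-distributed rates (means 0.5 to 2.0), weeks 3-8 as follow-up, and both readings of item 5. The drift was +0.03 to +0.49 CSBMs per week, and two-sided rejection was 19% to 100% at n = 280 (nominal 5%). With the three-month history limit imposed, the drift was +0.03 to +0.33 and rejection was again 19% to 100%. That set contains no case as low as a uniform rate of 0.3 and none with under-dispersed counts.

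**Between-arm comparison.** A two-sample t test on change, on the same kind of null data, rejected in 5.6% of trials. Randomisation balances the drift.

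**The case against.** The strongest reply is that no efficacy analysis uses this test. The sentence stands under general principles, names no outcome, and every outcome in 13.5 and 13.6 has its own between-group method, including comparisons at weeks 11-12, 15-16, 19-20 and 31-32. That part stands. A reader might infer that the plan will settle the sustained-effect objective by paired tests; it does not say so. What remains is that the sentence is operative, carries an alpha level, and is the only planned EA-only test for an objective that has no between-arm hypothesis.

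The second reply is about size, and it also stands. A reader might infer from the 99% that a false positive is close to certain. That needs widely spread rates, Poisson counts and the each-week reading. Nor does inflation vanish only when counts are less variable than Poisson: with all rates at 0.3 and full Poisson variation it is already small.

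Third, selection acts on CSBMs. Bias in straining, stool consistency or PAC-QOL would be indirect and has not been quantified. Stopping other constipation measures at the start of the run-in ("participants should discontinue laxatives or other medications and measures for constipation (except for rescue medicine") and patients' knowledge of their treatment could add further non-specific change, but nothing in the documents sizes either, and neither is in the figures above.

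**Conclusion.** The point holds as a limited one. Selection and baseline share the same two weeks, so for CSBMs the planned within-arm tests can be significant with no treatment effect. With Poisson counts and 280 per arm, the rate of false improvement ranges from about 4% to 99% on the each-week reading and from about 2.5% to 81% on the 2-week-average reading, against 2.5% nominal. These ranges rest on assumed rates and dispersion and cannot be narrowed from the documents.

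A reader might infer that the non-inferiority result is biased. It is not: the primary CMH analysis and the between-arm analyses in 13.6 compare randomised groups that share the same drift. The exposure is confined to a within-EA p-value being used to support the 3-6 month objective. The change should be made, but the main conclusion of the trial does not depend on it.

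**What to change.** In SAP 13.3:

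1. Delete "Comparisons with the baseline used paired t tests or nonparametric tests".
2. Report within-arm change from baseline as a mean or median with a 95% CI, descriptively and without p-values.
3. State that within-arm change is not by itself evidence that EA works or that its effect lasts, because patients were selected on the same run-in weeks and there is no sham or untreated arm.
4. Base efficacy statements, including those on sustained effect, on the randomised between-arm difference with its 95% CI in each window.

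The cost is a change of wording and the loss of within-arm p-values from the tables. It needs no new data and no additional patients.
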